### 2.3 Intention to treat (ITT) and per protocol (PP) analysis

We will apply a modified ITT principle, considering only the participants who started the antenatal stimulation and/or participated in the breastfeeding consultation and as the ITT population. Participants who drop out before the breastfeeding consultation for any reason will not be included in any of our analyses. We consider PP as all of the participants who completed questionnaires until 8 weeks post-partum, no matter how well they complied with the intervention. We will apply ITT and PP analysis to our primary and secondary outcomes.

## 3. Study design

### 3.1 Randomization

All participants will be randomized 1:1 into one of two arms: Group A aBME from week 34+0 or Group B no aBME. Randomization in this pilot trial will not be blinded to participants or investigators performing the data analysis due to the intervention type.

### 3.4 Withdrawal/dropout from the study

We will register the reason for withdrawal. We will divide withdrawal into the following categories:

1. Withdraw because of investigations in relation to the trial
2. Withdraw because of side effects in relation to the intervention
3. Withdraw because of time consumption in relation to the trial
4. Withdraw because of other reasons (will be described)
5. The participant is excluded from the trial because it is in the participant's best interest
6. The participant is excluded from the trial because the participant does not want to follow the instructions related to the randomization group
7. The participant is excluded from the trial due to loss of contact
8. The participant is excluded from the trial due to other reasons (will be described)

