In general the evidence in aBME is limited. A few prospective studies has been conducted, and only one larger RCT. This RCT included 635 participants, where aBME was performed from week 36 of pregnancy. They were not able to detect any difference in gestational age at birth or report any adverse events in relation to the aBME. Before the larger RCT they conducted a pilot study, which consisted of 43 participants. Our aim with this study is to primarily test safety and feasibility with the procedure aBME from week 34, and since no study has been done from this week of pregnancy, a reliable power calculation is not possible to make. Therefore we estimated that 30 participants in each group is a realistic and feasible number to include in the pilot study. To detect a difference in gestational age at birth based on 80% power, we estimated that we would need a total of 176 participants, 88 in each group (mean, SD, derived from Soltani et al(19)). If the pilot study shows no trend towards a higher proportion of preterm birth in the intervention group, we will proceed to the larger trial.

Data collection:

Demographic data on the mothers (maternal age, education level, ethnic background, parity and smoking status) will be obtained through medical files. Infant data on gestational age, complications such as preterm contractions or birth and feedings from birth, will be obtained from medical records after birth. To obtain data on aBME and breastfeeding rates after birth, we will use SMS tracking via an app based in the RedCap system. From intervention start until 8 weeks after birth participants in the intervention group will receive a weekly sms, with questions on how many times they stimulated and if they were capable of expressing any milk. The control group will receive a weekly message which regards if they have been giving birth, to be able to initiate the questions on breastfeeding. After birth questions will regard breastfeeding initiation. After eight weeks the mothers experience and evaluation on the study will be evaluated in an online questionnaire.

Data analysis and statistics:

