### 2.2 Adherence to the intervention

We consider all participants who answer weekly questionnaires until 8 weeks post-partum as full completers. E.g. if participants try to follow the intervention as well as possible, but do not stimulate the breast the recommended fourteen times a week, we will still consider them as completers of the study, if they have stayed in the study during the intervention and until eight weeks after birth. However, we will differentiate between study completion and intervention completion. Intervention completion is defined as participants who follow the intervention as well as possible until birth but do not answer all eight questionnaires. These participants will be included in the analysis for gestational age at birth, but will only be included in the breastfeeding analysis as long as they have answered the weekly questions. If participants do not want to perform stimulation anymore, we consider this as a withdrawal of consent. If participants are not adherent to the randomized group, e.g. they start to stimulate antenatal even though they are in the control group, we consider them as excluded from the study.

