## 4.2 Outcome measurement

### 4.2.1 Primary outcome

Safety: the primary outcome is gestational age at birth in the two groups. Median and interquartile range will be used due to the non-normality of this variable and non-parametric test (Ranksum test), to detect differences between groups.

A posterior plot for the probability of non-inferiority will be produced by Bayesian binomial regression with symmetric weakly informative priors.

Adverse events will only be reported for the intervention group as numbers and percentages: Bleeding, regular contractions, uterus pain, Braxton Hicks contractions, or others that will cover anything else. Self-reported by the women in the intervention group.

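### The SAP records women lost to contact as excluded from the trial, although gestational age comes from the medical record, and it does not say consistently whether they stay in the primary safety analysis.

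*SAP*

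**What the plan says.** SAP 3.4 opens with "We will register the reason for withdrawal. We will divide withdrawal into the following categories" and lists eight. The first four are reasons why a woman withdraws; the last four describe her being excluded. Category 7 is "The participant is excluded from the trial due to loss of contact". The SAP does not define loss of contact, for example by a number of missed messages.

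The primary outcome is set in SAP 4.2.1: "Safety: the primary outcome is gestational age at birth in the two groups". Its source is in the Protocol, Data collection: "Infant data on gestational age, complications such as preterm contractions or birth and feedings from birth, will be obtained from medical records after birth". Contact is needed for other data: "To obtain data on aBME and breastfeeding rates after birth, we will use SMS tracking via an app based in the RedCap system".

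Three other rules decide who is analysed:

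- **SAP 2.3, modified ITT:** "considering only the participants who started the antenatal stimulation and/or participated in the breastfeeding consultation". Anyone who drops out before the consultation is left out of all analyses.
- **SAP 2.3, per protocol (PP):** women who completed questionnaires to 8 weeks after birth, however well they complied. ITT and PP are both applied to the primary outcome.
- **SAP 2.2:** women who follow the intervention until birth but miss some questionnaires are kept for this outcome: "These participants will be included in the analysis for gestational age at birth".

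SAP 4.5 rules out imputation and uses the data available.

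**The concern.** A woman who stops answering has lost her message data. She has not lost her gestational age, and she has not withdrawn consent. Coding her as excluded invites the analyst to discard a safety value that sits in a record the team already consults.

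The Protocol commits to intention to treat, and its Sample Size section makes the larger trial depend on seeing no trend towards a higher preterm proportion in the intervention group. With 30 women per arm, that reading can turn on one or two births.

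Loss need not be equal between arms. The trial is unblinded, loss of contact has no definition, and the messages before birth differ: group A is asked about expression, group B whether the birth has happened. An early birth or a hospitalised infant could plausibly make a woman stop answering, but the documents contain no evidence on this.

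**Working it through.** **1. What each rule does to a silent woman**

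| When contact is lost | Modified ITT analysis | PP analysis of gestational age |
|---|---|---|
| Before the week-33 consultation | Out (2.3) | Out (2.3) |
| Between consultation and birth | In by 2.3, but excluded from the trial by 3.4; 2.2 does not clearly cover her | Out (2.3) |
| Between birth and 8 weeks, group A, following the intervention to birth | In by 2.2 and 2.3; 3.4 still labels her excluded | Out (2.3) |
| Between birth and 8 weeks, group B | In by 2.3; 2.2 is worded for women following the intervention; 3.4 labels her excluded | Out (2.3) |

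Loss is explicit in the first row and in the whole PP column. Elsewhere, the label in 3.4 conflicts with the set defined in 2.3.

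**2. Lost numbers matter less than selective loss**

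The plan has no figure for loss. Its one power figure is 88 per group for 80% power. The mean and SD behind it are not given, so it can only be inverted: at two-sided 0.05, d = (1.960 + 0.842)/√(88/2) = 0.422 SD. Power at n per arm is about Φ(0.422·√(n/2) − 1.960). This is 37.3% at 30 and 34.2% at 27 (assuming 3 lost per arm), a small fall.

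**3. How few events are involved**

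The documents give no preterm rate. For an assumed 3% to 10%:

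- Expected preterm births per arm: 30 × 0.03 = 0.9 to 30 × 0.10 = 3.0.
- If 3 women are lost at random (assumed), the chance that at least one had a preterm birth is 1 − (1 − p)³, or 8.7% to 27.1%.

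As an example, take 3/30 in group A v 1/30 in group B, a difference of +6.7 points. If two of the three early births are dropped, 1/28 v 1/30 gives +0.2 points. With Beta(1,1) priors and an assumed margin of 10 points, since the SAP states neither, the posterior probability of non-inferiority moves from 0.72 to 0.94.

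**4. Selective loss in each direction**

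Assumptions: true preterm proportion 10% in A and 5% in B; 10% of women with term births are lost; the loss among preterm births, l, is 30% or 50% where there is excess loss and 10% otherwise; every lost woman is dropped.

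Observed proportion = p(1 − l)/[p(1 − l) + (1 − p)(0.90)].

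- p = 10%: 0.070/0.880 = 8.0% (l = 30%); 0.050/0.860 = 5.8% (l = 50%).
- p = 5%: 0.035/0.890 = 3.9%; 0.025/0.880 = 2.8%.

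No trend is taken as an observed proportion in A no higher than in B. The chances come from simulation with 30 per arm; the all-kept value was also computed exactly (31.2%).

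| Scenario | Expected difference, A − B (points) | Chance of no trend |
|---|---|---|
| All kept | 5.0 | 31% |
| Random 10% loss, both arms | 5.0 | 26% |
| Excess loss in A only, l = 30% / 50% | 3.0 / 0.8 | 35% / 47% |
| Excess loss in both arms | 4.0 / 3.0 | 30% / 36% |
| Excess loss in B only | 6.1 / 7.2 | 22% / 17% |

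Random loss gives 26% rather than 31% because unequal denominators break ties. The effect of selective loss is therefore better read against 26%.

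**The case against.** The strongest reply is that 3.4 is a list for reporting reasons, not an analysis rule. Nothing in it deletes a gestational age. The analysis sets are in 2.3, where a woman who attended the consultation belongs to the modified ITT set whatever she answers later, and 4.5 uses the data available, which includes her record. Section 2.2 points the same way: missed questionnaires cost breastfeeding data, not gestational age.

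Much of this stands. A reader might infer that category 7 by itself removes every silent woman from the main comparison, or that 2.2 reserves the gestational-age analysis for women who followed the intervention. The text supports neither: 3.4 defines no analysis set, and 2.2 says who is kept without saying that nobody else is. If 2.3 governs, women lost after the consultation stay in the modified ITT analysis and the effect there is nil.

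The reply does not settle the point. Categories 5 to 8 describe a status given to the woman, and 2.2 uses similar language for controls who start to express. An analyst could reasonably drop a category 7 woman. Nor does the reply touch the two explicit losses in 2.3.

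A reader might also infer that the rule hides harm. The documents do not show this. They give no loss rate, no preterm rate and no link between silence and early birth. Excess loss in group B would push towards a false safety signal.

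**Conclusion.** The point holds as a conflict in the rules plus two explicit losses of obtainable safety data: women lost before the consultation, and all who stop answering before 8 weeks in the PP analysis. For women lost after the consultation, the SAP needs to say which section governs.

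Size and direction of any bias are unknown. Under the assumed rates the chance of seeing no trend runs from 17% to 47%, against 31% with all kept. That range depends wholly on the assumed rates, on which arm has the excess loss, and on every silent woman being dropped. It shows that the decision is sensitive to such losses, not that the trial will be biased. The change is worth making before analysis because the data can be obtained without contact and the correction is cheap.

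**What to change.** - Reword SAP 3.4 category 7 as *stopped answering messages (loss of contact)*, and state that this ends message follow-up only.
- State in SAP 2.2 and 2.3 that gestational age and other record-based data are taken from the medical record and analysed in the randomised arm for every randomised woman, including those lost before the consultation, unless she withdraws consent to use of her record. Only her message-based outcomes are then missing.
- State that the PP set for gestational age does not require questionnaires to 8 weeks.

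The cost is a few sentences in the SAP. The Protocol already takes these data from the medical record, so no new data source or participant contact is needed.

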### 3.5 Time schedule

Recruitment was initiated on August 31, 2022, and will stop when 60 participants are enrolled.

Participants are enrolled and followed up continuously until 8 weeks PP

## 4. Analysis

### 4.1 Baseline characteristics

We will check the distribution for all reported data. The distribution will be checked by QQ plots and histograms. The normally distributed data will be reported as mean and standard deviations (SD) and the non-normally distributed data will be reported as median and interquartile ranges (IQR). Categorical data will be reported as numbers (n) and percentages (%).

#### Demographic data on mothers

- Age (years)
- Educational level
- Partner status

#### Clinical features on the mother

- Body-mass index (BMI) (kg/m^2)
- Height (cm)
- Pre-gestational weight (kg)
- Smoker status
- Medications (yes/no), if yes what type of medication and doses
- Gestational age at inclusion

#### Breastfeeding consultation

- Received other breastfeeding counseling (yes/no)
- Breastfed as a child (yes/partially/no)
- Partner participating in breastfeeding consultation (yes/no)

Only intervention group:

- CTG before stimulation (normal, deviant, or pathological)
- CTG under stimulation (normal, deviant, or pathological)
- CTG after stimulation (normal, deviant, or pathological)

#### Antenatal breastmilk expression (weekly questionnaires)

- Did you perform abME this week (yes/no)
- If yes, how many times (amount of stimulations pr. week)
- Did you collect any milk (yes/no)
- If yes, how many milliliters (mL milk)

#### Clinical features on infants

- Gestational age at birth (weeks+days)
- Gender (boy/girl)
- Birthweight (g)
- Birth length (cm)
- Head circumference (cm)
- APGAR score at 1 min (0-10)

- APGAR score at 5 min (0-10)
- Enteral Nutrition PP if hospitalized
- Way of feeding PP if hospitalized
- IV-solutions PP if hospitalized

Breastfeeding rates up to 8 weeks PP (both groups, weekly questionnaires):

- Feeding the first 24 hours (Did your child get anything other than your milk, yes/no)
- Are you breastfeeding (yes/no)
- If yes (Partially or exclusively breastfeeding)

## 4.2 Outcome measurement

### 4.2.1 Primary outcome

Safety: the primary outcome is gestational age at birth in the two groups. Median and interquartile range will be used due to the non-normality of this variable and non-parametric test (Ranksum test), to detect differences between groups.

A posterior plot for the probability of non-inferiority will be produced by Bayesian binomial regression with symmetric weakly informative priors.

Adverse events will only be reported for the intervention group as numbers and percentages: Bleeding, regular contractions, uterus pain, Braxton Hicks contractions, or others that will cover anything else. Self-reported by the women in the intervention group.

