Data will be collected in order to meet the CONSORT guidelines for Randomized Controlled Trials. Comparability of the two groups by intention to treat analysis. Where data are normally distributed, comparison of means will be done using unpaired t-tests. If data are not normally distributed a non-parametric test for unpaired data will be used, eg. Mann-Whitney test or permutation test. Multivariate

analysis will be carried out, if data shows differences in maternal or infant characteristics possibly affecting outcome.

[Interruption of the trial](#)

The involved investigators can stop the trial if the protocol is not followed or unexpected adverse effects in relation to the aBME such as contractions, vaginal bleeding or overrepresentation of preterm birth in the intervention group. The investigators in charge can pull out participants if they find it irresponsible to continue due to side effects or new pregnancy related conditions, where aBME could be contraindicated. Participants can at any time retract their consent and stop the intervention.

[Patient insurance](#)

This trial is covered by the Patient Compensation Scheme and Labour Market Insurance.

[Publication](#)

All results, positive, negative as well as inconclusive results will be published.

[Possible clinical implication:](#)

We expect this initiative to have positive impact on both mother and infant with improved breastfeeding rates and mothers confidence with breastfeeding. If aBME from 34 weeks does not induce preterm birth, we aim to investigate if this procedure is safe earlier in pregnancy and especially among pregnant women at increased risk of preterm delivery. In the long term, this could increase the number of preterm infants fed exclusively MOM and possibly contribute to improved gut health and neurodevelopmental outcome for preterm infants.

Referencer

1. WHO/UNICEF. Global nutrition targets 2025: breastfeeding policy brief (WHO/NMH/NHD/14.7). Geneva: World Health Organization; 2014.

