## 2. Statistical Principles

### 2.1 P values and confidence intervals

We will consider a P value of < 0.05 as statistically significant with a significant level at 95%.

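### Gestational age at birth, the safety outcome, has no planned between-group difference with a confidence interval, and the preterm proportion that decides progression is in no outcome list

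*SAP*

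**What the plan says.** - **Gestational age.** SAP 4.2.1 labels gestational age at birth as safety. It plans medians, interquartile ranges and a "non-parametric test (Ranksum test), to detect differences between groups". SAP 2.1 has confidence intervals in its title, but its text sets only a threshold: "We will consider a P value of < 0.05 as statistically significant". The protocol's statistics section also names tests only.
- **Bayesian analysis.** SAP 4.2.1 adds: "A posterior plot for the probability of non-inferiority will be produced by Bayesian binomial regression with symmetric weakly informative priors". It does not state the binary event, the effect scale, the margin or range of margins, or the prior scale.
- **Progression.** Under Sample Size, the protocol says that if the pilot shows "no trend towards a higher proportion of preterm birth in the intervention group, we will proceed to the larger trial".
- **Preterm birth elsewhere.** Under Data collection, "complications such as preterm contractions or birth and feedings from birth, will be obtained from medical records after birth". Under Interruption of the trial, one reason to stop is "overrepresentation of preterm birth in the intervention group". The preterm proportion is in neither the protocol's outcome list nor SAP 4.2. Neither document gives a gestational-age cut-off for preterm, and the SAP text supplied does not use the word.
- **Blinding.** SAP 3.1 says that randomization will "not be blinded to participants or investigators performing the data analysis".
- **Size.** The pilot has 30 per arm, chosen on feasibility. For a comparison of gestational age at 80% power the protocol adds: "we estimated that we would need a total of 176 participants, 88 in each group".

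**The concern.** A safety pilot should tell its reader how large a harm the data exclude. Two medians and a P value do not, because the same P above 0.05 can accompany a narrow interval around zero or a wide one that includes a material shortening of pregnancy.

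The outcome that is tested is also not the one that decides what happens next. Gestational age and the preterm proportion can disagree: a small shift among term births moves the first and not the second, while a few more early births may barely move a median. So the deciding quantity needs its own estimate. As written, its definition and the meaning of 'no trend' could be settled by unblinded analysts after the counts are known. At stake is the decision to start the larger trial.

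**Working it through.** **1. The protocol's own figure.** The 176 cannot be reproduced, because the mean difference and SD behind it are not in the documents. It can be solved backwards. Inputs from the protocol: 88 per arm and 80% power. Assumed: a two-sided 5% comparison of means, since no sidedness is stated.

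d = (1.960 + 0.842) × √(2/88) = 0.422 SD

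The t-test version gives 0.425. One-sided 5% gives (1.645 + 0.842) × √(2/88) = 0.375 SD (0.376 by t-test).

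**2. What a P value can show at 30 per arm.** Power for 0.425 SD, two-sided 5%:

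| Method | Power |
|---|---|
| t-test | 0.37 |
| Rank-sum, normal shape (simulated) | 0.35 |
| Rank-sum, left-skewed, gamma shape 4 | 0.41 |
| Rank-sum, left-skewed, gamma shape 2 | 0.48 |

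Repeat runs put the rank-sum range at about 33% to 49%. If a difference of that size were real, P above 0.05 would be at least as likely as not.

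**3. What an interval would show.** t-based half-width: 2.002 × √(2/30) = 0.517 SD. The simulated median half-width of the Hodges-Lehmann 95% interval is 0.529, 0.485 and 0.440 SD for the three shapes above. All exceed 0.42 SD. In days, for assumed SDs of 1.0, 1.5 and 2.0 weeks, the t-based half-width is 3.6, 5.4 and 7.2 days, against 3.0, 4.4 and 5.9 days for 0.42 SD.

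**4. Preterm birth.** The counts are illustrative, as the documents give no rate. The Newcombe interval is built from the Wilson limits l and u of each arm. With equal counts its half-width is √[(p − l)² + (u − p)²].

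- 1/30 v 1/30: l = 0.0059, u = 0.1667; √(0.0274² + 0.1334²) = 0.136, or ±13.6 points.
- 2/30 v 2/30: l = 0.0185, u = 0.2132; √(0.0482² + 0.1466²) = 0.154, or ±15.4 points.

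**5. How much depends on 'no trend' (illustration only).** Exact binomial, 30 per arm, with the control rate assumed. Each cell is the chance of proceeding if any excess counts as a trend / if an excess of one birth is tolerated.

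| Control rate | No harm | Doubled risk |
|---|---|---|
| 2% | 71% / 93% | 49% / 77% |
| 3% | 66% / 88% | 41% / 66% |
| 5% | 62% / 82% | 31% / 51% |
| 6% | 61% / 80% | 28% / 45% |

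**6. How much the Bayesian reading depends on unstated settings (illustration only).** For 3/30 (intervention) v 1/30, in a logistic model with intercept N(0, 10) and log odds ratio N(0, 2.5), the probability that the risk difference lies below the margin is 0.15, 0.51 and 0.81 at margins of 0, 5 and 10 points. With N(0, 1) on the log odds ratio it is 0.23, 0.71 and 0.93.

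**The case against.** Several points on the other side stand.

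- **P above 0.05 read as safety.** A reader might infer that the plan will do this. No passage says so. Progression rests on the preterm proportion, and a separate non-inferiority analysis suggests that the authors did not rely on the rank-sum test alone.
- **No comparison of preterm birth at all.** This too would go too far. A binomial model under the safety outcome needs a two-category event, and preterm birth is the only candidate the protocol offers. What is missing is the name, the cut-off and the link to progression.
- **The absent margin.** A posterior plot may show the probability over a range of margins and leave the choice to the reader. The SAP does not say this, but it does not exclude it. The prior scale and the wording of 'no trend' are likewise largely missing detail.
- **It is a pilot.** The protocol says openly that no reliable power calculation was possible, so low power is not a fault here. A small sample makes an interval more useful, not less.
- **Limits of the figures.** Even with an observed difference of zero, failing to exclude 0.42 SD is near certain only for normal-shaped data. In the most skewed case it happens in about 55% to 61% of runs.
- **Limits of the text.** SAP numbering jumps from 3.1 to 3.4 and from 4.2.2 to 4.5, so statements of absence apply to the text supplied.
- **Bounded consequence.** A mistaken decision to proceed leads to a larger randomized trial. The protocol does not say that this pilot alone decides on work earlier in pregnancy or in women at higher risk.

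None of this supplies an interval for gestational age or an estimate for the preterm proportion.

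**Conclusion.** The concern holds in this form: the safety outcome has no planned between-group estimate with an interval, and the quantity that governs progression is in no outcome list, has no planned risk difference and is not tied to the one analysis that probably addresses it.

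The size is material. At 30 per arm the interval for gestational age reaches about 0.44 to 0.53 SD either side, wider than the 0.42 SD implied by the protocol's own larger-trial figure (0.38 SD if one-sided). The interval for preterm birth reaches about 14 to 15 points either side at one or two events per arm. These figures assume the stated test, shapes and counts. The proceed and posterior probabilities rest on rates, margins and priors that the documents do not give; they show only that the reading matters. The finding is about what is reported and how the decision is read, not about the sample size.

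**What to change.** In SAP 4.2.1, with matching wording in the protocol's Sample Size section:

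1. Beside the rank-sum P, report a between-group difference in gestational age in days with a 95% confidence interval (Hodges-Lehmann, or a difference in medians), and base the safety conclusion on the interval.
2. Name preterm birth as the event in the Bayesian model, with the sponsor's stated gestational-age cut-off (conventionally before 37+0). Report its counts and risk difference by arm with a Newcombe or score 95% interval.
3. State that the progression decision is read from that estimate and posterior. The sponsor should fix the meaning of 'no trend' before outcomes are compared by arm, or label it post hoc. No threshold is proposed here: a looser reading gives fewer false stops and more false proceeds, and that trade-off is the sponsor's.

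The cost is wording and two estimates from data already collected, with no extra participants. The downside is that the pilot must say openly that it excludes only large harms.
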